## 4. ANALYSIS POPULATIONS

| Population | Definition / Criteria                                                                                                                                                                                                                                               | Analyses Evaluated                                                         |
|-------------------|----------------------------------------------------------------------------------------------------------------------------------------------------------------------------------------------------------------------------------------------------------------------------|-----------------------------------------------------------------------------------|
| All Subjects      | 
 
• All subjects who receive at least one dose of study medication.
 
                                                                                                                                                        | 
 
• Demographic
 
• Safety
 
 |
| PK                | 
 
• Subjects in the "All Subjects" population for whom a PK sample was obtained and had evaluable PK assay results. PK samples that may be affected by protocol deviations will be reviewed by the study team to determine
 
 | 
 
• PK
 
                            |

| Population | Definition / Criteria                       | Analyses Evaluated |
|------------|---------------------------------------------|--------------------|
|            | whether or not the sample will be excluded. |                    |

**NOTES :**

- Please refer to Appendix 10: List of Data Displays which details the population to be used for each display being generated.

#### **4.1. Protocol Deviations**

- Important protocol deviations (including deviations related to study inclusion/exclusion criteria, conduct of the trial, patient management or patient assessment) will be summarised and listed.
- Protocol deviations will be tracked by the study team throughout the conduct of the study in accordance with the Protocol Deviation Management Plan.
  - Data will be reviewed prior to freezing the database to ensure all important deviations and deviations which may lead to exclusion from the analysis are captured and categorised on the protocol deviations dataset.
  - This dataset will be the basis for the summaries and listings of protocol deviations.
- A separate summary and listing of all inclusion/exclusion criteria deviations will also be provided. This summary will be based on data as recorded on the inclusion/exclusion page of the electronic case report form (eCRF).

## 5. CONSIDERATIONS FOR DATA ANALYSES AND DATA HANDLING CONVENTIONS

Table 1 provides an overview of appendices within the RAP for outlining general considerations for data analyses and data handling conventions.

**Table 1 Overview of Appendices**

| Section | Component                                                            |
|---------|----------------------------------------------------------------------|
| 10.1    | Appendix 1: Time & Events                                            |
| 10.2    | Appendix 2: Treatment States and Phases                              |
| 10.3    | Appendix 3: Data Display Standards & Handling Conventions            |
| 10.4    | Appendix 4: Derived and Transformed Data                             |
| 10.5    | Appendix 5: Premature Withdrawals & Handling of Missing Data         |
| 10.6    | Appendix 6: Values of Potential Clinical Importance                  |
| 10.7    | Appendix 7: Multiple Comparisons and Multiplicity                    |
| 10.8    | Appendix 8: Model Checking and Diagnostics for Statistical Analyses. |
| 10.9    | Appendix 9: Abbreviations and Trade Marks                            |
| 10.10   | Appendix 10: List of Data Displays                                   |

## 6. STUDY POPULATION ANALYSES

### 6.1. Overview of Planned Analyses

The study population analyses will be based on the “All Subjects” population, unless otherwise specified.

Table 2 provides an overview of the planned study population analyses, with full details of data displays being presented in Appendix 10: List of Data Displays.

**Table 2 Overview of Planned Study Population Analyses**

| Display Type                                       | Data Display's Generated |       |         |
|----------------------------------------------------|--------------------------|-------|---------|
|                                                    | Figure                   | Table | Listing |
| Enrollment                                  |                          |       |         |
| Number of Subjects Enrolled by Country and Site ID |                          | Y     |         |
| Randomisation                               |                          |       |         |
| Randomisation                                      |                          |       | Y       |
| Subject Disposition                         |                          |       |         |
| Subject Disposition                                |                          | Y     |         |
| Reasons for Screening Failures                     |                          | Y     | Y       |
| Reasons for Withdrawals                            |                          |       | Y       |
| Important Protocol Deviations                      |                          | Y     | Y       |
| Inclusion and Exclusion Criteria Deviations        |                          |       | Y       |
| Demography                                  |                          |       |         |
| Demographics Characteristics                       |                          | Y     | Y       |
| Race and Racial Combinations                       |                          | Y     | Y       |
| Age Ranges                                         |                          | Y     |         |
| Study Populations                                  |                          |       | Y [1]   |
| Concomitant Medications                     |                          |       |         |
| Concomitant Medications                            |                          |       | Y       |

**NOTES:**

- Y = Yes display generated.

1. Listing includes only subjects excluded from any population.

## 7. PRIMARY STATISTICAL ANALYSES

### 7.1. Pharmacokinetic Analyses

#### 7.1.1. Overview of Planned Pharmacokinetic Analyses

The PK analyses will be based on the PK Population, unless otherwise specified.

Table 3 provides an overview of the planned analyses, with full details being presented in Appendix 10: List of Data Displays.

**Table 3 Overview of Planned Pharmacokinetic Analyses**

| Display Type         | Untransformed  |   |   |         |                                    |                  |   |   | Ln-Transformed |   |   |         |   |            |   |   |
|----------------------|----------------|---|---|---------|------------------------------------|------------------|---|---|----------------|---|---|---------|---|------------|---|---|
|                      | Stats Analysis |   |   | Summary |                                    | Individual       |   |   | Stats Analysis |   |   | Summary |   | Individual |   |   |
|                      | T              | F | L | T       | F                                  | F                | L | T | F              | L | T | F       | F | L          | T | F |
| PK Concentrations    |                |   |   | Y       | Y 
 | Y  | Y |   |                |   |   |         |   |            |   |   |
| Plasma PK Parameters | Y              | Y |   | Y       | Y 
 | Y                | Y |   |                |   | Y | Y       |   |            |   |   |

**NOTES :**

- T = Table, F = Figure, L = Listing, Y = Yes display generated.
- Stats Analysis = Represents TFL related to any formal statistical analyses (i.e. modelling) conducted.
- Summary = Represents TFL related to any summaries (i.e. descriptive statistics) of the observed raw data.
- Individual = Represents FL related to any displays of individual subject observed raw data.

[1] Linear and Semi-Logarithmic plots will be created on the same display.

[2] Separate mean and median plots will be generated.

#### 7.1.2. Drug Concentration Measures

Refer to Appendix 3: Data Display Standards & Handling Conventions (Section 3 Reporting Process & Standards).

#### 7.1.3. Pharmacokinetic Parameters

##### 7.1.3.1. Deriving Pharmacokinetic Parameters

- Refer to Appendix 3: Data Display Standards & Handling Conventions (Section 3 Reporting Process & Standards).
- The PK parameters will be calculated by standard non-compartmental analysis according to current working practices and using Phoenix WinNonlin Version 6.4 or higher.
- All calculations of non-compartmental parameters will be based on actual sampling times.
- Pharmacokinetic parameters described in Table 4 will be determined from the plasma concentration-time data, as data permits.

**Table 4** **Derived Plasma Pharmacokinetic Parameters**

| Parameter | Parameter Description                                                                                                                                                                                                                                              |
|-----------|--------------------------------------------------------------------------------------------------------------------------------------------------------------------------------------------------------------------------------------------------------------------|
| AUC(0-t)  | Area under the concentration-time curve (AUC) from time 0 (predose) to time of the last quantifiable concentration, to be calculated using the linear trapezoidal rule for each incremental trapezoid and the log trapezoidal rule for each decremental trapezoid. |
| AUC0-24   | Area under the concentration-time curve (AUC) over time 0 (predose) to 24 hours after dose administration, to be calculated using the linear trapezoidal rule for each incremental trapezoid and the log trapezoidal rule for each decremental trapezoid.          |
| AUC(0-∞)  | Area under the concentration-time curve from time 0 (predose) extrapolated to infinite time, calculated as:
$AUC(0-\infty) = AUC(0-t) + Ct / \lambda z$ where Ct is the last observed quantifiable concentration.                                               |
| %AUCex    | The percentage of AUC(0-∞) obtained by extrapolation (%AUCex) will be calculated as:
$[\text{AUC}(0-\infty) - \text{AUC}(0-t)] / \text{AUC}(0-\infty) \times 100$                                                                                               |
| Cmax      | Maximum observed concentration, determined directly from the concentration-time data.                                                                                                                                                                              |
| Ct        | The last observed quantifiable concentration                                                                                                                                                                                                                       |
| C24       | The observed concentration at 24 hours after dose administration                                                                                                                                                                                                   |
| tmax      | Time to first occurrence of Cmax                                                                                                                                                                                                                                   |
| tlag      | Lag time before observation of drug concentrations in sampled matrix                                                                                                                                                                                               |
| t½        | Terminal phase half-life will be calculated as:
$t\frac{1}{2} = \ln 2 / \lambda z$                                                                                                                                                                              |
| λz        | Terminal-phase rate constant                                                                                                                                                                                                                                       |
| CL/F      | The apparent oral clearance                                                                                                                                                                                                                                        |
| Vz/F      | The apparent volume of distribution during the terminal phase                                                                                                                                                                                                      |

**NOTES:**

- Additional parameters may be included as required.

**7.1.3.2. Statistical Analysis of Pharmacokinetic Parameters**

The following PK statistical analyses will only be performed, if sufficient data are available (i.e. if subjects have well defined plasma profiles).

| Pharmacokinetic Statistical Analyses                                                                                                                                                                                                          |  |
|-----------------------------------------------------------------------------------------------------------------------------------------------------------------------------------------------------------------------------------------------|--|
| Endpoint(s)                                                                                                                                                                                                                            |  |
| 
 
Plasma primary PK endpoints include AUC(0-∞), AUC(0-t) and Cmax of DTG, as data permit
 
                                                                                                      |  |
| Model Specification                                                                                                                                                                                                                    |  |
| 
 
In Part 1 of this study, the ln-transformed AUC(0-∞), AUC(0-t), and Cmax values for DTG will be analyzed separately using a mixed effects model, fitting fixed effect terms for period, and
 
 |  |

| Pharmacokinetic Statistical Analyses                                                                                                                                                                                                                                                                                                                                                                                                                                                                                                                                                                                                                                                                                                                                 |
|----------------------------------------------------------------------------------------------------------------------------------------------------------------------------------------------------------------------------------------------------------------------------------------------------------------------------------------------------------------------------------------------------------------------------------------------------------------------------------------------------------------------------------------------------------------------------------------------------------------------------------------------------------------------------------------------------------------------------------------------------------------------|
| treatment, and treating subject as a random effect. Point estimates and 90% CIs for the differences of interest (conventional DTG 5 x 10 mg tablets administered direct to mouth [Treatment A, Test] versus conventional DTG 1 x 50 mg tablet administered direct to mouth [Treatment B, Reference]) will be constructed using the residual variance                                                                                                                                                                                                                                                                                                                                                                                                                 |
| 
 
In Part 2 of this study, the ln-transformed AUC(0-∞), AUC(0-t), and Cmax values for DTG will be analyzed separately using a mixed effects model, fitting fixed effect terms for period and treatment, and treating subject as a random effect. Point estimates and 90% CIs for the differences of interest (5 x 5 mg dispersible DTG tablets [Treatment C, Test 1] versus conventional DTG 1 x 25 mg tablet administered direct to mouth [Treatment E, Reference], and conventional DTG 5 x 5 mg tablets administered direct to mouth [Treatment D, Test 2] versus conventional DTG 1 x 50 mg tablet administered direct to mouth [Treatment E, Reference]) will be constructed using the residual variance.
 
       |
| Model Checking & Diagnostics                                                                                                                                                                                                                                                                                                                                                                                                                                                                                                                                                                                                                                                                                                                                         |
| 
 
Refer to Appendix 8: Model Checking and Diagnostics for Statistical Analyses.
 
                                                                                                                                                                                                                                                                                                                                                                                                                                                                                                                                                                                                                                      |
| Model Results Presentation                                                                                                                                                                                                                                                                                                                                                                                                                                                                                                                                                                                                                                                                                                                                           |
| 
 
Statistical analysis by ANOVA will be presented in tabular format with geometric mean ratios between TIVICAY™ conventional and dispersible tablets versus conventional DTG tablets, and 90% CIs for the ratios of AUC(0-∞), AUC(0-t) and Cmax for DTG.
 
 
Part 1 Example SAS Code:
 <pre>PROC MIXED; CLASS USUBJID TRTA APERIOD; MODEL LOGPKPARM =TRTA APERIOD /DDFM=KR; RANDOM USUBJID; LSMEANS TRTA; ESTIMATE 'A VS B' TRTA 1 -1/CL ALPHA=0.1;RUN;</pre> 
Part 2 Example SAS Code:
 <pre>PROC MIXED; CLASS USUBJID TRTA APERIOD; MODEL LOGPKPARM =TRTA APERIOD /DDFM=KR; RANDOM USUBJID; LSMEANS TRTA; ESTIMATE 'C VS E' TRTA 1 0 -1/CL ALPHA=0.1; ESTIMATE 'D VS E' TRTA 0 1 -1/CL ALPHA=0.1;RUN;</pre> |

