5.6. Dose Justification

The US Food and Drug Administration (FDA)-approved dose of DTG for treatment-naïve HIV-infected adult and pediatric patients 12 years and older (and ≥ 40 kilogram [kg]) is 50 mg once daily. The adult dose is given as 1x50 mg tablet once daily.

Part 1 of the study will compare relative BA of five 10-mg conventional tablets (test) to that of one 50-mg conventional tablet (reference). For part 1, the approved adult dose of 50 mg DTG conventional tablet is used as a reference to benchmark exposures with paediatric formulations to what is safe and effective in adults.

Part 2 of the study will compare relative BA of five 5 mg dispersible tablets administered as "disperse and immediately take" and of dispersible 5 mg tablets to be administered as "direct to mouth" to that of a single 25 mg conventional tablet (reference) administered direct to mouth. The 25 mg dose of DTG control dose used in Part 2 of this study will accommodate the relative BA assessment of the two pediatric dosage forms and will require a dosing of only five (5) 5 mg tablets, as opposed to 10 tablets that would have been necessary if the 50 mg DTG control dose would have been chosen for evaluation in Part 2 of the study. With respect to reference dose in Part 2 of this study, the 25 mg tablet is quantitatively proportional to the 50 mg tablet and hence two 25mg tablets are equivalent to 50 mg tablet. However, the 25 mg tablet was chosen as a comparator for this part so as to decrease the burden on the subjects to consume 10 x 5 mg tablets directly to mouth as well as to minimize any associated variability.

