| Overview of Study Design and Key Features |                                                                                                                                                                                                                                                                                                                                                                                                                                                                                                                                                                                                                                |
|--------------------------------------------------|--------------------------------------------------------------------------------------------------------------------------------------------------------------------------------------------------------------------------------------------------------------------------------------------------------------------------------------------------------------------------------------------------------------------------------------------------------------------------------------------------------------------------------------------------------------------------------------------------------------------------------|
|                                                  | 
 
• Treatment D: 5-mg dispersible DTG tablet (5 tablets) administered as direct to mouth (test 2).
 
• Treatment E: Conventional 25-mg DTG tablet administered as direct to mouth (reference).
 
                                                                                                                                                                                                                                                                                                                                                                          |

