### 10.3. Appendix 3: Data Display Standards & Handling Conventions

#### 10.3.1. Study Treatment & Sub-group Display Descriptors

| Treatment Group Descriptions |                 |                                                                                                      |                             |                      |
|------------------------------|-----------------|------------------------------------------------------------------------------------------------------|-----------------------------|----------------------|
| Study Part                   | Treatment Group |                                                                                                      | Data Displays for Reporting |                      |
|                              | Code            | Description                                                                                          | Description   | Order  |
| 1                            | A               | DTG conventional 10 mg tablets (5 tablets) administered direct to mouth (test)                       | Treatment A                 | 1                    |
| 1                            | B               | DTG conventional 50 mg tablet administered direct to mouth (reference)                               | Treatment B                 | 2                    |
| 2                            | C               | DTG dispersible 5-mg tablets (5 tablets) administered as a dispersion and immediately taken (test 1) | Treatment C                 | 3                    |
| 2                            | D               | DTG dispersible 5-mg tablets (5 tablets) administered direct to mouth (test 2)                       | Treatment D                 | 4                    |
| 2                            | E               | DTG conventional 25 mg tablet administered direct to mouth (reference)                               | Treatment E                 | 5                    |

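### Does the mislabelling of the tablets in the SAP's Part 2 D-versus-E contrast alter the primary analysis?

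*SAP*

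**What the plan says.** The Part 2 model paragraph in SAP 7.1.3.2 sets out two contrasts for ln-transformed AUC(0-∞), AUC(0-t) and Cmax. Treatment C is compared "versus conventional DTG 1 x 25 mg tablet administered direct to mouth [Treatment E, Reference". The second contrast names its test product as conventional, at 5 x 5 mg, and continues "tablets administered direct to mouth [Treatment D, Test 2] versus conventional DTG 1 x 50 mg tablet administered direct to mouth [Treatment E, Reference".

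SAP 10.3.1, which fixes the treatment descriptions for data displays, defines D as "DTG dispersible 5-mg tablets (5 tablets) administered direct to mouth (test 2" and E as "DTG conventional 25 mg tablet administered direct to mouth (reference". SAP 2.3 agrees with it, as do the SAP synopsis and Protocol 5.2 and 7.1. Protocol 5.6 gives the reason for the Part 2 reference: "the 25 mg tablet was chosen as a comparator for this part", so that subjects need not swallow ten 5 mg tablets. SAP 2.1 lists the departures from the protocol's analysis, and none concerns D or E.

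**The concern.** The sentence specifies the model for the primary endpoints, and it gives the reference treatment two strengths a few words apart. The D-versus-E contrast as worded is neither dose-matched nor a comparison of a dispersible with a conventional tablet, which is the question Part 2 asks. Part 2 has no 50 mg tablet, and neither document describes a conventional 5 mg tablet.

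If someone relied on the printed strengths, the reading of the result could shift by a factor of two. Under dose proportionality and equal bioavailability, 25 mg against 50 mg would centre on a ratio of 0.50 instead of 1.00. A reader who dose-normalised an observed D/E ratio of 1.00 with those strengths would report 2.00. The wording could also be copied into report text.

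**Working it through.** **1. The definitions side by side.**

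| Place | Treatment D | Treatment E |
|---|---|---|
| Protocol Synopsis, 5.2, 7.1 | five 5 mg dispersible tablets | one conventional 25 mg tablet |
| Protocol 5.6 | five 5 mg dispersible tablets | 25 mg, preferred to a 50 mg control |
| SAP 1, 2.3, 10.3.1 | five 5 mg dispersible tablets | one conventional 25 mg tablet |
| SAP 7.1.3.2, C versus E | not described | one conventional 25 mg tablet |
| SAP 7.1.3.2, D versus E | five 5 mg tablets, called conventional | one conventional 50 mg tablet |

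Only the last row differs. Protocol 9.2 also counts any Part 2 dose above 25 mg as an overdose. The odd row has the same form as the Part 1 A-versus-B wording (conventional tablets, five against one 50 mg tablet). That suggests text carried over from Part 1, though this is an inference.

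**2. Dose arithmetic.** D is 5 × 5 mg = 25 mg. Against E as defined elsewhere, the dose ratio is 25/25 = 1.0. Against E as printed in the odd row, it is 25/50 = 0.5.

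**3. What the program would estimate.** The Part 2 example code uses treatment codes only. With the levels sorted C, D, E, the coefficients `1 0 -1` give C minus E and `0 1 -1` give D minus E. Both are the contrasts named by letter in Protocol 10.1 and SAP 2.4. The 50 mg tablet is Treatment B in Part 1. Subjects take part in one part only (Protocol 5.1), and the parts are modelled separately, so no 50 mg observation can enter the Part 2 model.

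**4. The plan's own precision figure.** Inputs from Protocol 10.2.1: within-subject CV 16.2%, n = 18, 90% interval.

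- σ_w = √ln(1 + 0.162²) = 0.161.
- Residual degrees of freedom for the three-period model: 54 − 1 − 17 − 2 − 2 = 32.
- Log-scale half-width = t(0.95, 32) × σ_w × √(2/18) = 0.0909.
- Interval around 1: exp(∓0.0909) = (0.913, 1.095).
- With pairwise degrees of freedom, 18 − 2 = 16, the half-width is 0.0937 and the interval (0.911, 1.098).

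Both round to the protocol's (0.91, 1.10). The printed tablet strength enters none of these steps.

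**5. The hypothetical.** If a 50 mg reference had really been given, with dose-proportional exposure and equal bioavailability, the interval would be 0.50 × exp(∓0.0909), about (0.46, 0.55). That result requires data the trial does not collect.

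**6. Where a strength could enter a calculation.** SAP Table 4 lists no dose-normalised AUC or Cmax. CL/F and Vz/F do depend on dose. They are secondary parameters, are derived in the non-compartmental step before this model, and are not in the model tables, which SAP 10.10.5 limits to AUC(0-t), AUC(0-∞) and Cmax. Assuming their dose input is the dose given, the sentence in 7.1.3.2 does not touch them.

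**The case for a change.** The best case for acting is that a primary-analysis specification should not contradict itself, and that correcting it costs one line. The text is intact, and no declared change explains it. Read alone, the sentence makes C and D look like different products, when they are one tablet given in two ways. Displays label arms mainly by letter, so report prose has to take product descriptions from somewhere, and this paragraph is a possible source.

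The textual part of this stands: both labels disagree with every other definition. The claimed consequences do not. SAP 10.3.1 is the designated source for display labels and describes both treatments consistently with the protocol. The output for this contrast, Table 3.5 in SAP 10.10.5, has a title with no strength or formulation in it. A writer misled by the sentence would have to overlook the 25 mg given for E earlier in the same sentence, the letters attached to each product, and the treatment table. That could happen, but nothing in the documents points to it. The factor of two also needs a dose-normalisation step that the SAP does not plan.

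**Conclusion.** This is a clerical slip with no analytical effect. The treatment letters, the SAS contrast, the model, the sample size and the expected interval of (0.91, 1.10) all stay as they are, and the D/E ratio computed under the SAP would be identical with or without the wrong words. The wording of SAP 7.1.3.2 has to be reconciled with the treatment definitions in Protocol 5.2, SAP 2.3 and SAP 10.3.1. That is an editorial matter, not a change to the plan.

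The conclusion assumes that analysts work from the treatment codes, as the example code does, that display labels come from SAP 10.3.1, and that AUC and Cmax are not dose-normalised. The documents support the first two directly. The third rests on no such parameter being listed, although SAP 7.1.3.1 allows parameters to be added.
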